Using transesophageal echocardiography to evaluate the effect of levosimendan on patients with acute respiratory distress syndrome associated with right ventricular dysfunction during mechanical ventilation

numbering scheme ARVD20220810

version number V1

Version date 20220810

major investigators [name]

[figure not shown]
Estimated starting and ending  
date 2022.12.01-2025.12.01

Project abstract	
Research title	Using transesophageal echocardiography to evaluate the effect of levosimendan on patients with acute respiratory distress syndrome associated with right ventricular dysfunction during mechanical ventilation
Introduction	
Acute respiratory distress syndrome (ARDS) is often complicated by right ventricular dysfunction (RVD), the incidence can be as high as 64%. Acute cor pulmonale is the most serious form of ARDS complicated with RVD. The prognosis of ARDS patients with RVD is worse and the risk of death would be significantly increased. Currently, there are very limited clinical drug treatment options for RVD. Levosimendan is indicated for short-term treatment of acute decompensated heart failure that is not responding well to conventional therapy and requires increased myocardial contractile force. In 2016, the European Society of Cardiology issued recommendations for the management of acute right heart failure, stating that levosimendan can improve right ventriculo-pulmonary artery coupling by both increasing right heart contractility and reducing pulmonary vascular resistance. Levosimendan is therefore recommended to be given priority over dobutamine in the treatment of acute right heart failure. At present, there are also relevant clinical studies reporting that levosimendan can be used in acute right heart failure caused by different causes, including a single center randomized controlled study reporting that levosimendan can do work in the right ventricle of patients

	with sepsis ARDS, and has beneficial hemodynamic effects. However, the clinical application of levosimendan in the treatment of ARDS right heart dysfunction is insufficient. Therefore, this study intends to use transesophageal ultrasound to evaluate right ventricular function, reduce the limitation of poor right ventricular window in transthoracic echocardiography, and conduct a multi-center randomized controlled study to further explore the effects of levosimendan on right ventricular function in ARDS patients, such as tricuspid ring systolic displacement (TAPSE) and tricuspid ring systolic displacement velocity (S'). Effects of right ventricular area change fraction (RV FAC), right ventricular end-diastolic area/left ventricular end-diastolic area (RVEDA/LVEDA), pulmonary circulation resistance (PVR), RV-PA coupling, hemodynamics and mortality.
Study objective	To investigate the effects of levosimendan on the coupling of RVD, PVR, RV-PA, hemodynamics and mortality of ARDS patients with mechanical ventilation.
Study design	Prospective, multicenter, randomized controlled, clinical study.
Total number of patients enrolled	A total of 58 subjects are expected to be enrolled
Number of study groups	There were 29 cases in the experimental group and 29 cases in the control group.
Number of control groups	
diagnostic criteria	The diagnosis of ARDS is based on the 2012 Berlin definition

Inclusion criteria	
1) Patients who agree to participate in this clinical trial and sign informed consent;
 
2) Age 18-80 years old, gender unlimited;
 
3) Patients with ARDS requiring mechanical ventilation;
 
4) Acute right ventricular dysfunction due to ARDS;

Exclusion criteria	
1) Pregnant or lactating women;
 
(2) Chronic cardiac dysfunction, pulmonary hypertension and/or right ventricular enlargement caused by chronic cardiopulmonary disease, cardiogenic shock or after major cardiac surgery before ARDS;
 
3) right ventricular myocardial infarction;
 
4) Uncorrected hypotension, hypoxemia and hypercapnia, or acid-base balance disturbance
 
5) Mechanical ventilation driving pressure <math>\geq 18\text{cmH}_2\text{O}</math> before randomization
 
6) Rapid arrhythmia;
 
7) pericardial tamponade;
 
8) Pulmonary embolism;
 
9) severe renal insufficiency;
 
10) severe liver insufficiency;
 
11) Failure to sign informed consent;
 
12) known allergy to the test drug;
 
13) Patients who have participated in other clinical trials within 30 days

Intervention	Patients will be randomized to treatment group A: intravenously injected levosimendan 12.5mg with 5% glucose injection 50ml configuration at 2ml/h for 24h, or treatment group B: control group with 5% glucose injection 2ml/h for 24h.

Evaluation criteria: Primary endpoint: Secondary end point: Safety evaluation	Primary endpoint: The rate of RVD occurrence within 48 hours after randomization. secondary end points: 1) Changes in the following indexes were assessed 48h after random administration including : TAPSE, S ', RV FAC, RVEDA/LVEDA PVR, RV-PA coupling, CI, SVI, SVR, ScvO2 SOFA scoring 2) Mortality at 28 days after randomization and in hospital
Statistical Methods:	Sample size: 23 cases in the experimental group and 23 cases in the control group. Considering the 20% shedding rate, the statistical sample size was 29 cases in the experimental group and 29 cases in the control group, and a total of 58 subjects were enrolled.  Primary endpoints: incidence of RVD 48h after randomization  Safety endpoints:  Safety endpoints are those where subjects have severe adverse reactions related to the drug that are persistent and cannot be corrected according to the protocol
Study duration	2023.02-2025.12
Subject attendance time	From the time subjects were recruited to the time each subject completed all follow-up visits
Research unit/location	Wuhan Union Medical College Hospital, the First Affiliated Hospital of Zhengzhou University, Henan Provincial People's Hospital
Name, qualifications and contact information of the principal investigator	
	[name], [contact], has obtained the GCP Certificate

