### **1.4.2 Probability of injury**

the possibility of subject harm may involve adverse effects associated with levosimendan. Clinically possible adverse effects are increased heart rate or temporary and slight decrease in blood pressure, which can be treated with dose reduction or withdrawal and symptomatic management.

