### **1.4.3 Degree of injury**

An increase in heart rate or a temporary slight drop in blood pressure is considered mild injury and can be treated appropriately.

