### **7.2 Safety evaluation**

- (1) Vital signs, physical examination, laboratory examination indicators.
- (2) The incidence of adverse events/adverse reactions was evaluated according to CTCAE4.0 (Annex 4).
- (3) Incidence of serious adverse events/serious adverse reactions.

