## **9. Statistical analysis and statistical methods**

- (1) Case enrollment analysis: The total number of enrolled and completed cases in each center was listed, and three analytical data sets (FAS, PPS, SS) were determined. List the cases of shedding and elimination and their causes.
- (2) Demographic data and baseline analysis: descriptive demographic data and other baseline characteristic values; The number of cases, mean value, standard deviation, median, minimum value and maximum value of measurement data were calculated. Count and grade data calculation frequency and component ratio.
- (3) Effect analysis: CMH- $\chi^2$  test considering central effect was used for comparison between groups. t test or Wilcoxon rank sum test were used to compare the measures between groups.  $\chi^2$  test or Fisher's exact probability method were used to compare the classification indexes between groups. Rank data were obtained by Wilcoxon rank sum test or CMH- $\chi^2$  test. Survival data will be described using Kaplan-Meier curves and life tables. A nonparametric confidence interval for the median lifetime is calculated. Linear rank tests (logrank test and Wilcoxon test) were used to compare

survival between the treatment group and the control group. The Cox risk model was used to analyze the potential influence of covariates (predictors). Multivariate logistic regression was used to analyze dichotomous outcomes, such as recurrence rates, and this multivariate model would identify the most significant predictors. Logical or proportional advantage models will be used to adjust for prognostic factors. Precise confidence intervals will be calculated for the binary event incidence.

(4) Safety analysis: the incidence of adverse reactions was calculated; The sub-system lists the frequency and frequency of adverse reactions and calculates the percentage; A detailed list of adverse event cases; A detailed list of adverse event cases; The number and rate of "abnormal normal conversion" or "abnormal intensification" of laboratory indicators, electrocardiogram and physical examination after the test; List laboratory indicators, electrocardiograms, abnormal cases of physical examination and clinical explanations.

(5) Statistical software and general requirements use SAS software for analysis. All statistical tests were two-sided, and  $P \leq 0.05$  would be considered statistically significant.

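### The abstract's safety endpoint counts only severe, drug-related, persistent and uncorrectable reactions, which does not match sections 7.2, 8 and 9(4); one definition covering both arms is needed

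*Protocol*

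**What the plan says.** The only text that the protocol labels as safety endpoints is in the project abstract, under Statistical Methods. It restricts them to "severe adverse reactions related to the drug that are persistent and cannot be corrected according to the protocol". Section 2, which sets out objectives and endpoints, names primary and secondary endpoints and no safety endpoint.

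Section 7.2 describes the safety evaluation differently, in three items:

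- "Vital signs, physical examination, laboratory examination indicators"
- "The incidence of adverse events/adverse reactions was evaluated according to CTCAE4.0 (Annex 4")
- "Incidence of serious adverse events/serious adverse reactions"

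Section 9(4) opens the safety analysis with "the incidence of adverse reactions was calculated". It adds frequencies of adverse reactions by body system, a case listing of adverse events, and counts and rates of new or worsening laboratory, ECG and physical-examination abnormalities.

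Section 8 defines both adverse events and serious adverse events by reference to levosimendan treatment. It does not mention the glucose arm.

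On the harms to expect, section 1.4.2 names "increased heart rate or temporary and slight decrease in blood pressure, which can be treated with dose reduction or withdrawal and symptomatic management", and section 1.4.3 says that such an effect "is considered mild injury and can be treated appropriately". Section 5.1 sets out corrective steps for hypotension and tachycardia: fluids, pressors, and slowing or stopping the infusion until the problem has gone.

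**The concern.** A safety endpoint should be able to register the harms that the plan itself anticipates, and to compare them between arms. The abstract's version does neither well. Its persistence and correctability tests remove any episode that the section 5.1 steps put right. Its relatedness test makes the count depend on attribution to levosimendan, which a patient receiving glucose can hardly satisfy.

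At stake is how the safety result reads. If the abstract's endpoint is reported as the safety outcome, it can be close to zero in both arms while the adverse-event listing shows a difference. Nothing in the protocol says which definition governs, so the choice could be made after the data are seen.

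**Working it through.** The protocol states no figure on this point. The check is a comparison of the texts, followed by a simple bound.

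**Step 1. The definitions side by side.**

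| Place | What is counted | Must be severe? | Must be drug-related? | Must be persistent and uncorrectable? | Arms |
|---|---|---|---|---|---|
| Abstract, Statistical Methods | Reactions | Yes | Yes | Yes | Not stated |
| Section 7.2 | Vital signs, examination, laboratory; adverse events/reactions by CTCAE 4.0; serious adverse events/reactions | No | No | No | No limit |
| Section 8 | Adverse events; serious adverse events | Only for the serious category | No (stated for adverse events) | No | Levosimendan only |
| Section 9(4) | Incidence: adverse reactions. Listing: adverse events. Rates: laboratory, ECG, examination changes | No | Yes for the incidence, if reaction means a related event | No | Not stated |

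These are four different outcomes, with no statement of precedence.

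**Step 2. The anticipated harms against the abstract's four tests.**

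- *Fall in blood pressure as sections 1.4.2 and 1.4.3 describe it:* slight, temporary, mild, treatable. It fails on severity, persistence and correctability.
- *Increased heart rate as described there:* mild and treatable. It fails on severity and correctability. Section 1.4.2 calls only the blood-pressure fall temporary, so persistence is left open for heart rate, but failing one test is enough.
- *A larger episode of the kind that section 5.1 provides for:* it may be severe. If it resolves after the section 5.1 steps, it has been corrected under the protocol and fails the last test.
- *A severe, drug-related episode that persists despite those steps:* it passes all four tests and counts.

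**Step 3. What the endpoint can record.** Let n be the patients per arm, r the proportion with an episode, and c the proportion of those episodes that the section 5.1 steps correct. The abstract's endpoint records at most

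n × r × (1 − c).

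From section 3.2, n = 29. The protocol gives neither r nor c, so both are assumptions:

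- r = 20%: 29 × 0.20 = 5.8 patients with an episode. The endpoint records at most 5.8 if c = 0, and 0 if c = 1.
- r = 5%: 29 × 0.05 = 1.45 patients with an episode. The endpoint records at most 1.45 if c = 0, and 0 if c = 1.

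The count falls towards zero as c approaches 1, whatever r is. The endpoint therefore says least about how often the harm occurs when the corrective steps work best. Section 7.2 would count n × r in every case, provided that each episode is reported as an adverse event.

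**Step 4. The comparison between arms.** The abstract requires relation to the drug. The incidence in section 9(4) is again for reactions. Section 8 ties event definitions to levosimendan treatment. Together these leave the control count open to being low by definition, so a difference between arms would be hard to interpret.

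**The case against.** The strongest reply is that the body of the protocol already handles this. Section 7.2 grades adverse events without the four tests, section 9(4) lists adverse-event cases and gives rates for laboratory, ECG and examination changes, and section 6 records vital signs during treatment and for the first 24 hours after it. A patient with a severe but reversible pressure fall is an adverse event under section 7.2, and a serious one under section 8 if the fall is life-threatening and occurs on levosimendan. This stands, and it limits the consequence.

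A reader might infer three stronger things that the documents do not support:

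- *That the trial would miss a safety signal altogether.* The events are still collected, graded and listed.
- *That hypotension and tachycardia can never meet the abstract's endpoint.* A severe, related episode that resists correction would.
- *That the endpoint would show 0 versus 0 patients.* That result requires assuming that every episode is reversible (c = 1 above), and the protocol gives no such figure.

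It can also be said that the abstract's sentence, in translated English, was meant as a reason for ending participation. Section 6 does end participation for serious reactions related to the trial. But the sentence is labelled as safety endpoints and sits under Statistical Methods, so it needs rewording on either reading.

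Finally, section 7.2 pairs events with reactions, so the narrower word in section 9(4) may be loose drafting and not a deliberate restriction. That is possible. As written, though, section 9(4) provides an incidence for reactions and only a listing for events.

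**Conclusion.** The protocol defines its safety outcome inconsistently, and the version labelled as the endpoint is the least informative one. Reversible hypotension and tachycardia fall outside it. The incidence in section 9(4) is narrower than section 7.2, and section 8 leaves out the control arm. The harm is a headline endpoint that can read near zero and a weak between-arm comparison, not loss of data.

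The inconsistency is read directly from the text and rests on no assumed rate. That the endpoint would read near zero assumes that most episodes are corrected by the section 5.1 steps, as section 1.4.2 suggests. How far the relatedness test distorts the comparison depends on who judges causality and whether they know the arm; the protocol does not say that they are blinded.

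This should be corrected, as the definition is wrong as stated and cheap to put right. It does not bear on the sample size or the primary endpoint.

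**What to change.** Make three changes of wording:

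1. **Abstract, Statistical Methods:** replace the safety endpoint with the section 7.2 definition. If the present sentence was meant as a reason for ending participation, move it and label it so.
2. **Section 9(4):** compute, by arm, the incidence of all adverse events and of serious adverse events, whatever the judged relation or reversibility. Report drug-related reactions as a subset and keep the case listings.
3. **Section 8:** reword the definitions of adverse and serious adverse events so that they apply to both arms. Without this, adopting section 7.2 alone does not secure a fair comparison.

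Reporting by arm the proportion of patients whose infusion was reduced or interrupted would be a useful optional addition. The protocol does not state that infusion changes are recorded, so it might need a field on the case report form.

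The three core changes build on the safety evaluation already set out in section 7.2. The extra effort is to report events in the glucose arm on the same terms, if section 8 is currently read literally. One small downside is that the reported safety rate will look less favourable. No dosing or management rule is changed.

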#### The list of abbreviations

abbreviations	Benelux
ARDS	acute respiratory distress syndrome
RVD	Right ventricular dysfunction
TEE	Transesophageal ultrasound
FAC	Right ventricular area change fraction
PVR	Pulmonary circulation resistance
RV-PA	Right ventriculo-pulmonary artery coupling

## 1. Introduction

### 1.1 Background

#### 1.1.1 General Overview

Acute Respiratory Distress Syndrome (ARDS) is often complicated with Right Ventricular Dysfunction, Acute pulmonary heart disease is the most serious form of ARDS complicated with RVD. The pathogenesis includes pulmonary vascular dysfunction and right ventricular systolic dysfunction. Excessive inflammation, hypoxic pulmonary vasoconstriction, hypercapnia, pulmonary hyperventilation or collapse leading to increased pulmonary vascular resistance, pulmonary capillary microthrombosis and pulmonary vascular remodeling are important factors leading to ARDS right heart dysfunction. Meta-analysis has shown that patients with ARDS combined with RVD have worse prognosis and significantly increased risk of death, and RVD is not an independent risk factor for death in patients with COVID-19 ARDS [1-3]. RVD also occurs frequently in patients with COVID-19 related ARDS, and its incidence is even higher than the incidence of left heart dysfunction, and the fatality rate of patients with RVD increases significantly from 30.6% to 56.3%[4,5]. Despite the implementation of right cardiac protective mechanical ventilation, the incidence of RVD in ARDS patients is still as high as 21%[6]. It can be seen that the adjustment of mechanical ventilation strategy cannot completely solve RVD in ARDS patients. RVD can often lead to low cardiac displacement and hemodynamic failure in patients, resulting in increased mortality [7].

Currently, there are very limited clinical drug treatment options for RVD. The clinical indication for the use of levosimendan is for short-term treatment of acute decompensated heart failure that does not respond well to conventional therapy and requires increased myocardial contractile force. In 2016, the European Association of Cardiology issued recommendations on the management of acute right heart failure, indicating that levosimendan can improve right ventriculo-pulmonary artery coupling by increasing the right heart contractile force and reducing pulmonary vascular resistance, so it is recommended that levosimendan should be given priority over

dobutamine in acute right heart failure [8]. At present, relevant clinical studies have reported that levosimendan can be used in acute right heart failure caused by different causes, including a single-center randomized controlled study that reported that levosimendan can do work in the right ventricle of patients with septic ARDS, and has beneficial hemodynamic effects [9,10]. However, there is limited clinical experience in the treatment of right-heart dysfunction in patients with ARDS on mechanical ventilation and lack of high-quality clinical evidence. Therefore, multi-center randomized controlled studies are needed to obtain more and higher level of clinical evidence support, so it is necessary to carry out this clinical study.

In addition, the ratio of right ventricular end-diastolic area to left ventricular end-diastolic area (RVEDA/LVEDA) was used to evaluate ARDS RVD in the past, but this index cannot fully reflect right ventricular dysfunction. Right Ventricular Fractional Area Change (RV FAC) is significantly correlated with right ventricular end-diastolic area, and is more reflective of right ventricular systolic function [11]. In addition, lateral systolic displacement (TAPSE) of the tricuspid ring is also an important indicator of right ventricular systolic function. Therefore, in this study, RV expansion (RVEDA/LVEDA  $> 0.6$ ), TAPSE  $< 16\text{mm}$ , tricuspid ring systolic S 'velocity (TS  $< 10\text{cm/s}$ ) or RV FAC  $< 35\%$  represented RVD, and the incidence of RVD was used as the primary outcome indicator. Due to the poor right voice window in patients with mechanical ventilation, the evaluation of right heart function is limited. Therefore, from the perspective of practicality and operability in critical care medicine, this study uses transesophageal ultrasound to minimize the influence of lung gas on the right ventricular window, evaluates the right ventricular function in patients with mechanical ventilation ARDS, and discusses the influence of levosimendan on ARDS RVD and its relationship with prognosis, hoping to provide evidence support and useful reference for drug treatment of ARDS associated RVD.

## 1.2 Research Types

Prospective, multicenter, randomized controlled study.

## 1.3 Research Basis

Clinical studies have shown that inhaled pulmonary vasodilators such as NO and prostaglandins can reduce pulmonary circulatory resistance, improve pulmonary ventilation/perfusion ratio, and improve right cardiac function in ARDS patients [12]. Levosimendan is a calcium-sensitizer that relaxes blood vessels by increasing myocardial contractility while opening up adenosine triphosphate (ATP) -sensitive potassium channels in smooth muscle cells. Therefore, theoretically, levosimendan can improve the function of the right heart by increasing the systolic force of the right heart and reducing the Pulmonary Vascular Resistance (PVR) at the same time, and levosimendan has no significant effect on the ratio of pulmonary/systemic resistance [13]. Levosimendan has been widely used in acute decompensated left heart failure. Levosimendan has been shown to reduce right ventricular afterload and improve right cardiac function in animal models of right heart failure caused by acute pulmonary hypertension such as hypoxic pulmonary constriction, pulmonary artery ligation, and pulmonary embolism. In addition, levosimendan can also increase coronary blood flow, and has anti-proliferative and anti-inflammatory effects in animal models of chronic pulmonary hypertension, which can reduce pulmonary vascular remodeling [9,10]. Therefore, we speculate that levosimendan may be a beneficial clinical choice whether RVD occurs in the early or late stage of ARDS, and whether RVD in ARDS is due to impaired right heart function or elevated pulmonary circulation resistance.

At present, only one small sample single-center randomized controlled study has reported that levosimendan can relax the pulmonary vessels in patients with sepsis ARDS, improve the right ventricular - pulmonary artery (RV-PA) coupling in patients with pulmonary hypertension, improve the right ventricular work, and have beneficial hemodynamic effects [14]. However, the limitation of this study is single-center, small sample size, and MRI detection of right heart function may lead to some severe ARDS patients undergoing mechanical ventilation therapy unable to go out for cardiac MRI examination, resulting in selection bias. Therefore, this study intends to use transesophageal ultrasound to evaluate right heart function, reduce the limitation of poor right voice window in transthoracic echocardiography, and conduct a multicenter randomized controlled study to further explore the effects of

levosimendan on RVD, PVR[15], RV-PA coupling, hemodynamics and mortality in ARDS patients [16].

